5.1. Demographics and Baseline Characteristics

Patient demographics and baseline characteristics will be summarized by group based on the FAS population.

Assessments made before the first dose of cemiplimab will be used as baseline measurements for the purposes of statistical analysis and reporting unless otherwise specified.

5.2. Medical History

Medical history will be listed which includes SOC, PT, investigator verbatim and start and end dates and summarized by SOC and PT. Tables will be sorted by decreasing frequency of SOC followed by PT.

Cancer diagnosis will be listed and summarized by primary cancer diagnosis, histological grade and stages.

Prior cancer related surgery will be listed including type of procedure and date of surgery and summarized by prior surgery status. Prior cancer related systemic therapy will be listed including systemic therapy type, name of drug and start and end dates and summarized by systemic therapy type. Prior cancer related radiotherapy will be listed by site, total dose and start and end dates and summarized by prior radiotherapy status.

5.3. Prior/Concomitant Medications

Prior/concomitant medications will be listed including generic name and ATC levels 2 and 4, indication, study day onset (for medications started before treatment, the study day onset is defined as date of medication start - date of the first dose; for medications started on or after treatment, the study day onset is defined as date of medication start - date of the first dose+1), the study end date (defined similarly as for study onset day), ongoing status, dose, frequency, and

route. Number and proportion of subjects taking concomitant medications sorted by decreasing frequency of ATC Level 2 and ATC level 4.

5.4. Subject Disposition

For subject disposition, the following summaries by table will be provided:

- The total number of screened patients
- The total number of patients in each analysis set
- The total number of patients who discontinued the study treatment and the reasons for the treatment discontinuation
- The total number of patients who discontinued the study, and the reasons for the study discontinuation

Listing of patient disposition will include dates of the first and the last cemiplimab administration, date of the end of treatment and end of study visits, and reasons for treatment and study discontinuation.

5.5. Protocol Deviation

Protocol deviations will be defined in a separate protocol deviation definition document. A listing of all patients with protocol deviations and the reason of deviation will be provided. The major protocol deviation, such as violation of inclusion/exclusion criteria; post-enrollment deviations which will impact assessment of efficacy or safety endpoints, will be determined before database lock and be summarized by group.

5.6. Measurement of Compliance

Compliance with cemiplimab treatment will be calculated as follows:

Treatment Compliance =

$$\frac{\text{(Number of doses of cemiplimab administered during treatment period)}}{\text{(Number of doses of cemiplimab planned to be administered during period)}} \times 100\%$$

where temporary dose discontinuation is ignored.

The percentage of subjects who have <60%, 60-80%, 80-100%, and >100% compliance will be summarized for each group.

5.7. Exposure to Investigational Product

Exposure to cemiplimab will be examined for each subject and the following variables will be summarized by group:

- The total number of study doses administered
- The total dosage of cemiplimab administered

- Duration of treatment exposure (in weeks) calculated as the minimum of
 - [date of last dose - date of first dose + 14 days based on Q2 weekly dosing schedule] / 7 for Group 1 and Group 2;
[date of last dose - date of first dose + 21 days based on Q3 weekly dosing schedule] / 7 for Group 3, Group 5, and Group 6;
[date of last dose - date of first dose + 28 days based on Q4 weekly dosing schedule] / 7 for Group 4
 - or
 - [date of clinical data cut-off or date of death - date of first dose + 1] / 7
- The number and percentage of subjects exposed to cemiplimab will be presented by specific time points of interest (eg, . 4, 8, 12, 16, 24, 48, 72, 84, 96) for each group.
- The actual dose intensity (mg/kg/week) = total dose received per kg (mg/kg) / duration of treatment exposure (week) for Group 1 and Group 2;
The actual dose intensity (mg /week) = total dose received (mg) / duration of treatment exposure (week) for Group 3, Group 4, Group 5, and Group 6.
- The relative dose intensity = actual dose intensity / planned dose intensity,
 - Planned dose intensity (mg/kg/week) = planned dose (mg/kg) / 2 for Group 1 and Group 2;
 - Planned dose intensity (mg /week) = planned dose (mg) / 3 for Group 3, Group 5, and Group 6;
 - Planned dose intensity (mg /week) = planned dose (mg) / 4 for Group 4

For patients who also receive cemiplimab as re-treatment which starts more than 30 days after their last regular cemiplimab treatment, the retreatment dose will not be included in summary of on-treatment exposure, instead, they will be listed and summarized if necessary.

For Group 6 patients who opt to switch to SC cemiplimab, cumulative exposure to cemiplimab (IV + SC combined) and exposure to SC or IV alone will be summarized.

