1.2.5. Revision History for SAP Amendments

This is the sixth version of the SAP, based on the study protocol R2810-ONC-1540 Amendment 9 dated Sep 9, 2021.

The changes from SAP v5.0 dated Mar 10, 2021 (based on protocol amendment 7) include the addition of exploratory objectives and analysis for Group 6 patients who were allowed to switch to subcutaneous (SC) dosing per protocol amendment 9.

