Group 6 patients will receive up to twelve 63-day (9-week) treatment cycles for up to 108 weeks of treatment. Each patient will receive 350 mg cemiplimab intravenously on days 1, 22±3, and 43 ±3 during each treatment cycle. Tumor assessments will be made at the end of each treatment cycle. Extensive safety evaluations will occur on day 1 of each cycle, with routine safety evaluations to be conducted at each cemiplimab dosing visit. After implementation of PA9, patients will be given the option to receive subsequent doses of cemiplimab SC. The first 12 patients who opt to switch to SC will receive cemiplimab [REDACTED]. The next ≥6 patients who opt to switch to SC will receive cemiplimab [REDACTED]. Group 6 patients will have the option to switch to SC dosing or to remain on 350 mg Q3W IV dosing.

A patient will receive treatment until the treatment period (96 weeks in Group 1 and Group 2; 54 weeks in Group 3; 48 weeks in Group 4; 54 weeks in Group 5; 108 weeks in Group 6) is complete, or until disease progression, unacceptable toxicity, withdrawal of consent, or confirmed complete response (CR). Group 1 and Group 2 patients with confirmed CR after a minimum of 48 weeks of treatment and Group 6 patients with confirmed CR after a minimum 54 weeks of treatment may elect to discontinue treatment and continue with all relevant study assessments (eg, efficacy assessments).

Groups 1 through 5: Patients in all groups who do not experience progressive disease (PD) will be followed for an additional nontreatment period of up to approximately 6 months with scans performed every 8-12 weeks. After completion of this follow-up period, patients will then enter an extended follow-up period for approximately 1 additional year with assessments every 4 months. Patients in Groups 1 to 5 who complete treatment without disease progression and subsequently experience disease progression during the follow-up period without any intervening systemic anticancer therapy, are eligible for up to 2 years of retreatment with cemiplimab 350 mg IV Q3W.

Group 6: Patients who do not experience PD at the completion of the planned treatment period will enter follow-up for approximately 6 months. There is no extended follow-up for Group 6. Patients enrolled in Group 6 are not eligible for retreatment.

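### SAP 5.7 applies three-weekly exposure terms to all of Group 6, and they do not fit patients who switch to six-weekly subcutaneous dosing

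*SAP*

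**What the plan says.** SAP 5.7 opens: "Exposure to cemiplimab will be examined for each subject and the following variables will be summarized by group". The list covers duration of exposure, actual dose intensity (total dose over duration) and relative dose intensity (RDI, actual over planned).

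- **Duration.** For Groups 3, 5 and 6 it is the smaller of "date of last dose - date of first dose + 21 days based on Q3 weekly dosing schedule] / 7" and a cap, "date of clinical data cut-off or date of death - date of first dose + 1] / 7".
- **Planned intensity.** "Planned dose intensity (mg /week) = planned dose (mg) / 3 for Group 3, Group 5, and Group 6".
- **Other groups.** Groups 1 and 2 use +14 days and a divisor of 2; Group 4 uses +28 days and a divisor of 4.
- **Switchers.** For Group 6 patients who move to SC dosing, "cumulative exposure to cemiplimab (IV + SC combined) and exposure to SC or IV alone will be summarized". No separate formula is given.

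The formula text is not redacted, and it makes no exception for route or interval. SAP 1.2.5 says that this version brings in "the addition of exploratory objectives and analysis for Group 6 patients who were allowed to switch to subcutaneous (SC) dosing".

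Protocol Appendix 3 has separate PK schedules for a switch to three-weekly SC and a switch to six-weekly SC; the latter has predose samples on Days 1 and 43 of the SC cycle. SAP 2.3 describes two SC regimens, both redacted: "The first 12 patients who opt to switch to SC will receive cemiplimab" one of them, and the next 6 or more receive the other.

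**The concern.** In every other case the added days and the divisor equal the dosing interval of the regimen. For six-weekly SC they do not, although this SAP version was issued to cover the switchers. Followed literally, the rule credits only three weeks of exposure to a dose meant to cover six, and compares intensity with a plan on a three-week clock. Planned dose is also undefined after a switch. At stake are the duration and dose-intensity summaries for the SC switchers, whose purpose is to extend experience with repeated SC dosing.

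**Working it through.** **Inputs.** Added days, divisors and cap: SAP 5.7. Dosing days: Protocol Tables 3, 4, 5 and 7. Six-weekly interval (42 days): Protocol Appendix 3. Switcher numbers: SAP 2.3; Group 6 size 167: SAP 2.2.

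**1. Reproduce the plan's totals.** Duration = (last dose day - first dose day + interval)/7.

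- Groups 1 and 2: last dose on day 11×56+43 = 659, so (658+14)/7 = 96 weeks.
- Group 3: last dose on day 5×63+43 = 358, so (357+21)/7 = 54 weeks.
- Group 4: last dose on day 5×56+29 = 309, so (308+28)/7 = 48 weeks.
- Group 6, all IV: last dose on day 11×63+43 = 736, so (735+21)/7 = 108 weeks. With 36 doses, RDI = (36/108)/(1/3) = 100%.

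All four match the planned durations, so the convention is last dose plus one interval of that regimen.

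**2. Duration with six-weekly SC.** Take k SC doses on schedule, with the cap not binding.

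- SAP rule, SC alone: (42(k-1)+21)/7 = 6k-3 weeks.
- Interval-matched: (42(k-1)+42)/7 = 6k weeks.

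After c nine-week IV cycles, the combined figures are 9c+6k-3 and 9c+6k. The gap is 3 weeks in each case.

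**3. Effect of the cap.** Let g be the days from the last dose to cut-off or death. Shortfall = min(42, g+1) - min(21, g+1) days:

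| g (days) | Shortfall (days) |
|---|---|
| 20 or less | 0 |
| 21 | 1 |
| 40 | 20 |
| 41 or more | 21 |

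Combined duration has no shortfall if the patient is back on three-weekly IV by the last dose, which Protocol 3.1.1.1 allows after notifying the medical monitor.

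**4. RDI with planned dose read as the six-weekly dose D.** For a fully compliant patient over the SC period, RDI = [kD/(6k-3)]/(D/3) = k/(2k-1), whatever D is: 100% at k=1, 66.7% at 2, 57.1% at 4 and 51.9% at 14. Interval-matched, it is [kD/(6k)]/(D/6) = 100% throughout.

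**5. RDI with planned dose read as 350 mg.**

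- SC period: (D/350)×k/(2k-1).
- IV and SC combined: (9c+3kD/350)/(9c+6k-3).

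Both equal 100% only if D = 350(2k-1)/k, which is 525 mg at k=2, 612.5 mg at k=4 and 675 mg at k=14. The value rises with k, so no fixed dose gives 100% at every k. These are algebraic break-even points, not candidate doses.

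**6. Changing only one term.** +42 days with a divisor of 3 gives 50% at every k. +21 days with a divisor of 6 gives 2k/(2k-1), from 200% at k=1 to 103.7% at k=14.

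**7. Reach.** Six-weekly switchers are either 12 (12/167 = 7.2%) or at least 6 (6/167 = 3.6%), depending on which redacted regimen is six-weekly.

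**The case against.** The strongest reply is that +21 days reproduces the protocol's own totals for switchers. Protocol Table 8 footnote b plans 108 weeks, or 111 after an even number of IV cycles. Six-weekly doses after 3, 5, 7 or 9 IV cycles can have a last dose at week 105, and adding 3 gives 108. After 4, 6, 8 or 10 cycles the last dose can fall at week 108, and adding 3 gives 111. On this view +42 days would report more weeks than planned.

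The fit is not decisive. The 111 needs a dose given when 108 weeks are already complete. Adding 6 weeks also yields 108 (last dose at week 102, even cycles) and 111 (last dose at week 105, odd cycles), with the parity reversed. It also agrees with 3 IV cycles plus the footnote's maximum of 7 SC cycles at 12 weeks each: 27+84 = 111. What stands is that the planned totals are ambiguous, so the shortfall is measured against the SAP's convention and not against an undisputed protocol total.

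A second reply is that the SC dose can be inferred. Protocol 5.1 gives 175 mg/mL and 2 mL injections, and Protocol 6.3.4.1 mentions a series of 3 injections for one regimen. If that regimen is the six-weekly one, D = 175×2×3 = 1050 mg and the 350 mg reading gives 3k/(2k-1), always above 100%. This is an inference about redacted text. It would settle the direction of the error on that reading but would not remove the error.

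It is also fair that switchers are not overlooked: SAP 5.7 gives them their own summaries. But the rule it states for Group 6 is the three-weekly one.

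**Conclusion.** The point holds, at minor weight. For a patient whose last dose is six-weekly SC, the rule leaves exposure up to 3 weeks short by the SAP's own convention. On neither reading of planned dose does a compliant six-weekly patient's RDI stay at 100%; on the 350 mg reading the direction depends on the redacted dose. Only descriptive exposure and dose-intensity summaries are affected, for 12 or at least 6 planned switchers. Objective response rate, dose counts, total dosage and compliance (SAP 5.6) do not use these terms. All-IV patients and three-weekly SC switchers are handled correctly.

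A reader might go further in two ways that the documents do not support:

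- That most six-weekly switchers will have understated exposure. No distribution of the time from last dose to cut-off or death is given, and the full loss needs at least 41 days.
- That required SC-alone RDI figures, or counts exposed at the listed time points for SC alone, will be wrong. SAP 5.7 does not expressly ask for either by route. The SC-period RDI values above illustrate the misfit; they are not promised outputs.

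Assumptions: the six-weekly interval is taken from the unredacted labels in Protocol Appendix 3, and doses are given on schedule.

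**What to change.** In SAP 5.7:

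- Take the end-of-exposure term from the regimen of the last dose in the period summarised: +42 days for six-weekly SC, +21 days for three-weekly IV or SC.
- Set the planned-intensity divisor by the regimen of each period: 6 for six-weekly SC, 3 for three-weekly IV or SC. Change both terms together.
- Define planned dose as the protocol-assigned dose of each period.

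Before fixing total planned weeks for combined IV and SC intensity, the sponsor should reconcile two sets of protocol passages: SC cycle length (12 weeks in Table 8 footnote a and one Appendix 3 label, 9 weeks in another Appendix 3 label) and total planned duration (108 or 111 weeks in Table 8 footnote b). This review takes no position on which is right.

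The cost is a few SAP lines and a small programming change, with no new data. The change is optional to minor in priority.

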5.8. Analyses of Efficacy Variables

The analysis of efficacy data will be performed based on the FAS. The summary of efficacy results will be presented by group.

5.8.1. Analysis of Primary Efficacy Variable

The ORR according to central review will be summarized by group and the corresponding 2-sided 95% exact binomial confidence intervals will be derived using the Clopper Pearson method (Clopper, 1934). BOR will also be summarized by group.

The primary analysis of efficacy is based on the exact binomial confidence interval approach of ORR. If the lower limit of 95% confidence interval of observed ORRs excludes 15% for Group

1 and Group 3, excludes 25% for Group 2, exclude 20% for Group 4, or exclude 28% for Group 6, the study treatment is deemed effective for that group, respectively.

In addition, ORR along with two-sided 95% exact binomial confidence intervals for all patients treated with cemiplimab will be presented. ORR in patients whose CSCC disease has been confirmed by central pathology review will also be summarized.

A sensitivity analysis will be performed for ORR using patients who received at least one dose of cemiplimab.

For Group 6 patients who opt to switch to SC cemiplimab, efficacy data per central review will be censored at the first SC dose. Because Group 6 patients are only allowed to switch to SC cemiplimab after completing at least 27 weeks on study (3 tumor assessments after baseline), which is the pre-specified timepoint for primary efficacy analyses in Group 6, switching to SC dosing will have no impact on the primary efficacy analysis for Group 6.

The primary endpoint of ORR will also be summarized by pooling the objective response observed in CSCC patients in this study with object response data of CSCC patients in Regeneron study R2810-ONC-1423 to satisfy regulatory requirements from certain regions. Details will be provided in separate SAP for integrated efficacy analysis.

5.8.2. Analysis of Secondary Efficacy Variables

ORR derived from the overall response that is based on investigator-reviewed evaluation will be analyzed similarly as primary efficacy variable.

DOR: The distribution of DOR will be estimated using the Kaplan-Meier method. The median DOR along with its 95% CI will be presented by group and Kaplan-Meier estimates with 2-sided 95% CIs at specific time points (eg, 4, 6, 8, 12, 16, 20 and 24 months) will be summarized. The Kaplan-Meier curves will be displayed by group. DOR will also be summarized descriptively by range. Number and percentage of patients with DOR at specific time periods of interest (eg, ≥ 4 months, ≥ 6 months, ≥ 8 months, ≥ 12 months, etc.) will be summarized by group.

PFS: The distribution of PFS will be estimated using the Kaplan-Meier method. The median PFS along with its 95% CI will be presented by group and Kaplan-Meier estimates with 2-sided 95% CIs at specific time points (eg, 4, 6, 8, 12, 16, 20 and 24 months) will be summarized. The Kaplan-Meier curves will be displayed by group.

OS: The distribution of OS will be estimated using the Kaplan-Meier method. The median OS along with its 95% CI will be presented by group and Kaplan-Meier estimates with 2-sided 95% CIs at specific time points (eg, 4, 6, 8, 12, 16, 20 and 24 months) will be summarized. The Kaplan-Meier curves will be displayed by group. A variant of OS defined by censoring patients at the start date of subsequent therapy will be summarized and displayed by Kaplan-Meier approach as a sensitivity analysis.

TTR will be summarized descriptively by group and at specific time periods of interest (eg, < 2 months, 2 to 4- months, 4 to 6- months, ≥ 6 months).

CR rate, DCR and dDCR with 95% confidence interval will be summarized by group using the Clopper-Pearson method.

Depth of tumor response will be displayed using waterfall plot and spider plot and summarized by descriptive statistics.

For Group 6 patients who opt to switch to SC cemiplimab, ORR, DOR, PFS per investigator assessment will be summarized as IV + SC combined period and IV period.

Absence of residual CSCC in biopsy samples from patients with locally advanced CSCC achieving a clinical response to cemiplimab, as measured by independent central pathological review, will be summarized descriptively.

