- Group 3: This cohort opens after the completion of enrollment to Group 1 and is for patients with metastatic CSCC. As was the case for Group 1 patients, Group 3 patients are required to have metastatic disease. As in Group 1, Group 3 includes patients with both nodal metastatic and distant metastatic disease. Group 3 patients receive cemiplimab 350 mg IV Q3W for up to 54 weeks (whereas patients in Groups 1 and 2 received cemiplimab 3 mg/kg IV Q2W for up to 96 weeks).
- Group 4: This cohort enrolls patients with advanced CSCC (metastatic [nodal or distant] or locally advanced). Group 4 only begins enrollment after completion of enrollment in Groups 1 through 3. The dose regimen is cemiplimab 600 mg IV Q4W for up to 48 weeks.
- Group 6: This cohort enrolls patients with advanced CSCC (metastatic [nodal or distant] or locally advanced). The dose regimen is cemiplimab 350 mg IV Q3W for up to 108 weeks. After implementation of PA9, patients will be given the option to receive subsequent doses of cemiplimab SC. [REDACTED]

[REDACTED] Group 6 patients who switch to SC dosing must:

- Have completed ≥ 27 weeks of study treatment and completed ≥ 3 tumor assessments on treatment, without disease progression
 - Patients may switch to SC dosing on Day 1 of next cycle, after completing Cycle 3 through Cycle 11 of IV dosing. Switching to SC dosing prior to completion of Cycle 3 of IV dosing is not permitted. Switching to SC cemiplimab after starting Cycle 11 Day 1 of IV dosing is not permitted. Switching to SC dosing mid-cycle is not permitted in any cycle.
 - Note: It is possible that study treatment doses may be missed in clinical studies for a variety of reasons. For patients who miss doses in Cycles 1-3, the minimum IV exposure requirement is 7 doses (of 9 planned in Cycles 1-3) without disease progression prior to switching to SC cemiplimab.
- Have provided written informed consent to switch to cemiplimab SC
 - Patients may sign the consent for SC dosing at-or-after the Cycle 3/Day 22 visit (ahead of the C4D1 visit). The investigator must confirm there has not been

disease progression at the end-of-cycle tumor assessment before the patient commences SC dosing.

- Have not missed ≥ 2 doses of IV cemiplimab therapy during the first 27 weeks. (Patients who have missed multiple IV doses may not be able to adhere to the SC schedule of events).

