4.5.2. Secondary Efficacy Variables

ORR based on investigator-assessed evaluation is also derived from the overall response that is based on investigator-assessed evaluation at each time point at which a response assessment occurs using the RECIST version 1.1 (Appendix 1 of the protocol) or the composite response criteria (Appendix 2 of the protocol).

Duration of response (DOR) is determined for patients with best overall response of CR or PR. Duration of response is measured from the time measurement criteria are first met for CR/PR (whichever is first recorded) until the first date of recurrent or progressive disease (radiographic or photographic), or death due to any cause. DOR by central-reviewed evaluation is the key secondary endpoint.

Patients who do not have a documented tumor progression or death will be censored at the last evaluable tumor assessment.

Progression-free survival (PFS) is measured from the start of treatment until the first date of recurrent or progressive disease (radiographic or photographic), or death due to any cause. Patients who do not have a documented tumor progression or death will be censored at the last evaluable tumor assessment. If a patient has no post-baseline tumor assessment, the patient will be censored at the first treatment date.

Overall survival (OS) is measured from the start of treatment until death due to any cause. Patients who do not have a survival event will be censored at the last date that patient is documented to be alive. As many patients may receive subsequent therapy after disease progression, a variant of OS will also be defined as censoring patients who do not have a survival event at the first date of a subsequent therapy is taken.

Time to tumor response (TTR) is determined for patients with BOR of CR or PR. TTR is measured from the start of treatment until the time measurement criteria are first met for CR/PR (whichever is first recorded).

For all of the above time-to-event variables, the time to event (day) is the date of event/censor the date of first study treatment+ 1.

CR rate is determined by the proportion of patients with best overall response of CR. Patients with best overall response of NE will be considered as not reaching an objective response of CR.

Disease control rate (DCR) is determined by the proportion of patients with BOR of CR, PR, or SD.

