Per sample size calculation, 167 patients are planned for Group 6. An interim analysis of Group 6 patients will be performed after the first 50% of patients have had the opportunity to be followed up for a minimum of 28 weeks (27 weeks for 3 tumor assessments + 1-week assessment window) or have reached the end of study. The interim analysis will include a minimum of 20 locally advanced CSCC patients. If 20 locally advanced patients are not yet enrolled in the set of the first 84 patients enrolled in Group 6, the interim analysis will be performed after 20 locally advanced CSCC patients have been enrolled and have had the opportunity to be followed for at least 28 weeks. All patients enrolled in Group 6 who have had the opportunity to be followed for at least 28 weeks will be included in the interim analysis.

For regions where alpha spending is not required: For this planned interim analysis, the ORR and associated 95% confidence interval will be summarized. As the primary objective of this interim analysis is point estimation on ORR and characterizing the precision of point estimation, there is no hypothesis testing associated with this interim analysis. Therefore, Type I error adjustment is not applicable for this planned interim analysis.

For regions where alpha spending is required: The overall type I error rate for analyses of the primary endpoint of ORR is controlled at a 2-sided alpha of 0.05 using the O'Brien-Fleming spending function. [Table 1](#) demonstrates the bound and boundary properties for ORR hypothesis testing at interim and final analyses, assuming interim analysis was performed at 50% of

enrollment. The table will be updated using the actual number of patients included in the interim and final ORR analysis.

Table 1: Alpha Spending for Analysis of ORR on Group 6 Patients

Analysis		Value
Interim Analysis ^a	Z	2.9626
	α (2-sided ^a)	0.0031
Final Analysis	Z	1.9686
	α (2-sided)	0.0490

^a As a 2-sided test is used at interim, the superiority or futility of cemiplimab treatment will be claimed if the statistical boundary is crossed.

For the interim analysis of ORR, the precision of ORR will be estimated by adjusted 2-sided 99.69% exact confidence interval. The un-adjusted 2-sided 95% exact confidence interval will also be reported at the time of interim analysis. The ORR of 28% for Group 6 will be excluded using the lower limit of 99.69% exact CI if the observed ORR is 44.1% or more (Table 2).

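### SAP 5.8.2 measures PFS for Group 6 SC switchers from treatment start, although only patients with about 27 weeks free of progression may switch

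*SAP*

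**What the plan says.** SAP 5.8.2 has one sentence on Group 6 patients who opt for SC dosing: for them, "ORR, DOR, PFS per investigator assessment will be summarized as IV + SC combined period and IV period". It gives no separate time origin for this subset and does not say when the IV period ends. The general definitions in SAP 4.5.2 therefore apply. For PFS: "Progression-free survival (PFS) is measured from the start of treatment until the first date of recurrent or progressive disease". DOR starts when response criteria are first met. Kaplan-Meier estimates are planned at time points such as 4, 6, 8, 12, 16, 20 and 24 months.

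Protocol 3.1.1.1 sets the conditions for switching. Patients must "Have completed ≥ 27 weeks of study treatment and completed ≥ 3 tumor assessments on treatment, without disease progression", and "Switching to SC dosing prior to completion of Cycle 3 of IV dosing is not permitted". The investigator must also rule out "disease progression at the end-of-cycle tumor assessment before the patient commences SC dosing". Protocol 1.1.1 expects about 18 patients to be offered the option.

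The only stated rule for efficacy data at the switch is in SAP 5.8.1 and Protocol 9.5.2. It censors central-review data at the first SC dose and does not cover the investigator-assessed summaries.

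**The concern.** Entry to this subset depends on the outcome that is then summarised, as judged by the same assessor. A patient who progresses or dies before the switch is never a switcher. Starting the PFS clock at treatment start credits each switcher with time during which no event could have been recorded.

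The stake is interpretation. Central-review data stop at the first SC dose, so these are the efficacy summaries specific to switchers and the ones most likely to be read as SC efficacy. Set beside Group 6 as a whole, they would look better even if SC and IV dosing worked identically.

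**Working it through.** **1. Minimum event-free time.** SAP 2.3 gives the cycle length: "Group 6 patients will receive up to twelve 63-day (9-week) treatment cycles for up to 108 weeks of treatment". Tumors are assessed at the end of each cycle, so three assessments take 3 × 9 = 27 weeks. This agrees with SAP Section 8: "27 weeks for 3 tumor assessments + 1-week assessment window". In months, 27 × 7 = 189 days and 189 / 30.4375 = 6.2. Visit windows can shorten this slightly. Protocol Table 7 requires at least 60 days between successive Day 1 visits, so the extreme is 3 × 60 = 180 days, or 180 / 30.4375 = 5.9 months.

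**2. IV period.** Assume it ends at the first SC dose. An investigator-assessed progression or a death before that date makes the patient ineligible to switch. PFS events are therefore 0 of about 18 and the median is not estimable. A DOR event is also a progression or death, so IV-period DOR has no events either. A simulation of 400,000 patients per assumed median, with switches at random between weeks 27 and 90, gave 0 IV-period events, as it must.

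**3. Combined-period PFS.** Let S(t) be PFS in unselected patients, t0 the switch time, and suppose SC dosing changes nothing. For switchers, S(t | switch at t0) = 1 for t ≤ t0 and S(t)/S(t0) for t > t0. The documents give no Group 6 PFS rate, so I assume exponential PFS, S(t) = 0.5^(t/m), with median m of 6, 12 or 24 months. For m = 12 and t0 = 6.2 months (week 27), S(t0) = 0.699 and S(12) = 0.50, so 12-month PFS in switchers is 0.50 / 0.699 = 0.72. By the memoryless property, the switchers' median from treatment start is m + 6.2.

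| Assumed median (months) | 4-month PFS, all vs switchers | 6-month PFS, all vs switchers | 12-month PFS, all vs switchers | Switcher median from treatment start | Switcher median from first SC dose |
|---|---|---|---|---|---|
| 6 | 63% vs 100% | 50% vs 100% | 25% vs 51% | 12.2 | 6 |
| 12 | 79% vs 100% | 71% vs 100% | 50% vs 72% | 18.2 | 12 |
| 24 | 89% vs 100% | 84% vs 100% | 71% vs 85% | 30.2 | 24 |

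The last column shows that starting the clock at the first SC dose recovers the assumed median.

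**4. Later switches.** Week 27 is a floor. Protocol 1.2.1 says Amendment 9 takes effect only after the data cut for the primary analyses, so some patients will switch well after week 27. A switch at week 54 guarantees 54 × 7 / 30.4375 = 12.4 months, which makes 12-month PFS 100% as well. A switch at week 90 guarantees 20.7 months. In the simulation of step 2, 12-month PFS in switchers was 78.1%, 90.4% and 95.5% for medians of 6, 12 and 24 months, against 25%, 50% and 71% in all patients.

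**5. DOR and ORR.** For a patient who responds before switching, the guaranteed DOR time runs from first response to the switch. ORR has no clock. Its denominator excludes patients who progressed early, so it estimates P(response | no progression at the switch). This exceeds the overall ORR if responders are more likely than non-responders to be progression-free at 27 weeks. The documents give no inputs to size this, so I attach no figure.

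**The case against.** The strongest objection concerns the population. SAP 5.8 analyses efficacy on the FAS by group, and the switcher sentence in SAP 5.8.1 is a rule about which data to include. Read the same way, the sentence in 5.8.2 would mean that all-Group-6 investigator results are shown with and without SC-period data. No selection bias would then arise. However, the sentence names the patients who opt to switch, and SAP 5.7 and 5.9.1 use the same opening for summaries of switchers alone. The switcher-only reading is the more natural one. What stands is that the population should be stated outright.

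It is also fair to say that no comparison of switchers with other patients and no test is planned, that the switcher objectives are labelled exploratory, and that both documents state the 27-week condition. That limits the weight of the point. It does not make the from-start figures informative about SC dosing.

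A reader might infer more than the documents support:
- These are not the only efficacy tables with SC-period data. Censoring at the switch is stated for central review only, so group-wide investigator DOR and PFS, and OS, include SC-period data by default.
- Immortal time does not affect all three endpoints alike. DOR starts at response, and ORR is affected by selection.
- The IV-period column is not wholly empty. IV-period ORR is in effect response status at the switch, and its difference from combined-period ORR shows later conversions.
- Zero IV-period events is not an absolute rule. The SAP does not define the end of the IV period, Protocol 3.1.1.1 allows a return to IV dosing, and an eligibility deviation or a revised progression date could produce an event.

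**Conclusion.** The point holds for switcher PFS and, in a different form, for DOR and ORR. The 100% PFS at 4 months follows from eligibility alone. At 6 months it follows from the nominal 27-week schedule; the shortest permitted schedule, 5.9 months, changes nothing material. The empty IV-period PFS and DOR also require that the IV period end at the first SC dose. The 12-month contrasts and the medians depend on exponential PFS, an assumed median and no SC effect. They show the direction and rough size of the artefact and do not predict trial results. They also ignore scan timing, and Protocol Table 8 gives 12-week SC cycles.

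This is a flaw in a small descriptive summary of about 18 patients. A reader might infer that the primary result is compromised. It is not: the primary ORR uses central review on all of Group 6, and no one may switch before three assessments. The change is still worth making because a better time origin is available at little cost.

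**What to change.** Amend SAP 5.8.2 for Group 6 patients who switch to SC dosing:

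- State that the summary covers switchers only, and define the IV period as ending at the first SC dose.
- Measure PFS from the first SC dose.
- Estimate DOR with delayed entry: a patient who responded before switching joins the risk set at the switch, and one who responds afterwards joins at response.
- Drop IV-period PFS and DOR for switchers.
- Keep IV-period ORR, label it response status at the switch, and show later conversions.
- Present combined-period results measured from treatment start on all Group 6 patients only. The group-wide investigator analyses largely provide this already.
- Note beside the table that switchers were selected on at least 27 weeks without progression.

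The cost is SAP wording and re-programming of one set of tables. The downside is shorter follow-up times and no from-start PFS figure for about 18 patients. With so few patients, the delayed-entry DOR curve will rest on small risk sets at early times, so the number at risk should be shown.
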